Table 5. Tasks Included in Memory Composite score, the Primary outcome

Table 6. Digital cognitive tests included in the secondary cognitive outcome

Table 7: Protocol-required Safety Laboratory Tests

Figure 1: Study Schema (Randomization and Treatment Pathway)

Figure 2: FDA Framework for Pre-Clinical and Clinical AD Stages

Figure 3: CONSORT Flow Diagram (Patient Throughput)

List of Abbreviations

Abbreviation	Definition
A β	Amyloid-beta
A β 1-40	Amyloid-beta 1-40
A β 1-42	Amyloid-beta 1-42
AChE	Acetylcholinesterase
AChEI	Acetylcholinesterase Inhibitor
AD	Alzheimer's Disease
ADL	Activities of Daily Living
AE	Adverse Event
ALT	Alanine Aminotransferase
APP	Amyloid Precursor Protein
AST	Aspartate Aminotransferase
AUC	Area Under the Curve
BDNF	Brain-Derived Neurotrophic Factor
bd	Twice daily (bis die)
CI	Coordinating Investigator
CRF	Case Report Form
CSF	Cerebrospinal Fluid
CSSRS	Columbia-Suicide Severity Rating Scale
CTCAE	Common Terminology Criteria for Adverse Events
CYP3A4	Cytochrome P450 3A4
DSMB	Data Safety Monitoring Board
ECG	Electrocardiogram
eCRF	Electronic Case Report Form
EV	Eudravigilance
FDG-PET	Fluorodeoxyglucose Positron Emission Tomography
FLAME	Factors of Longitudinal Attention, Memory, and Executive Function - validated computerized tests
FSH	Follicle Stimulating Hormone
GCP	Good Clinical Practice
GLP	Good Laboratory Practice
IB	Investigator's Brochure
IEC	Independent Ethics Committee
INR	International Normalized Ratio

Abbreviation	Definition
IRB	Institutional Review Board
IUD	Intrauterine Device
IUS	Intrauterine System
MCI	Mild Cognitive Impairment
MoCA	Montreal Cognitive Assessment
Nfl	Neurofilament Light Chain
NIA	National Institute on Aging
NIH	National Institutes of Health
od	Once daily (omni die)
PD	Pharmacodynamic
PET	Positron Emission Tomography
PK	Pharmacokinetic
PPI	Patient and Public Involvement
PROTECT	An online cohort study platform
P-Tau	Phosphorylated Tau
p-tau	Phosphorylated Tau
p-tau217	Phosphorylated Tau 217
qds	Four times a day (quater die sumendus)
RCT	Randomized Controlled Trial
rCBF	Regional Cerebral Blood Flow
rCMRGlc	Regional Cerebral Metabolic Rate for Glucose
SAE	Serious Adverse Event
SOP	Standard Operating Procedure
SUSAR	Suspected Unexpected Serious Adverse Reaction
TDS	3 times a day (ter die sumendum)
Tmax	Time to Maximum Concentration
t1/2 elim	Half-Life of Elimination
ULN	Upper Limit of Normal
WHO	World Health Organization
WOCBP	Woman of Childbearing Potential

1. Protocol Summary

In this open-label Phase 1b study, eligible participants with early or mild Alzheimer's disease (AD) will be randomized 6:2 to receive phenserine or donepezil for a total treatment duration of 8 weeks. Participants will dose escalate at 2- to 4-week intervals (depending on their treatment assignment) to achieve a maintenance dose level that is well tolerated. The objectives of the study are to characterize phenserine's pharmacodynamic activity in comparison to donepezil as evaluated by changes in exosome biomarkers and effects on cognition. In addition, safety, tolerability and pharmacokinetic assessments will be evaluated. The data from the study will be used to select an appropriate dose range for a subsequent Phase 2 proof-of-concept study to characterize phenserine's efficacy and safety in people with early or mild Alzheimer's Disease (AD) over a longer treatment duration.

The protocol is further summarized in the following synopsis and in the study schema that is presented in Figure 1. In addition, a detailed Schedule of Activities is presented in Table 1.

1.1. Synopsis

Protocol Title:

A phase 1b dose range finding study of Phenserine compared to Donepezil in participants with early or mild Alzheimer's disease.

Brief Title: Phenserine on the Alzheimer's Treatment Horizon, Study 1

Participants will be randomized into two groups: one group will receive phenserine, and the other will receive donepezil. The phenserine group will begin with a dosage of 5 mg twice daily, with the dose being gradually increased every two weeks as tolerated until the maximum dose of 10 mg three times daily is reached. The donepezil group will start at 5 mg once daily, with the possibility of escalation to 10 mg once daily at Week 4, again aiming for a 45% cholinesterase inhibition as tolerated.

The study is designed to last 8 weeks, with a planned total enrollment of 16 individuals from various centers across Norway. Participants will return for follow-up visits every two weeks, during which pharmacodynamic, pharmacokinetic, and safety assessments will be conducted. The final safety follow-up will occur after the completion of dosing for those who complete the study. Early termination visits will include a comprehensive safety follow-up for those who discontinue the study prematurely.

The primary objective of this study is to assess the effects of phenserine compared to donepezil on exosome biomarkers of cell death in individuals with early or mild AD. Additionally, the study aims to evaluate the safety and tolerability profile of phenserine at ascending doses up to 10 mg three times daily (TDS) in comparison to donepezil at doses up to 10 mg once daily (OD). Furthermore, the study aims to analyze steady-state blood levels of phenserine to characterize and compare dose-response relationships for pharmacodynamic outcomes and key safety assessments. Finally, the study will explore changes in specific biomarkers of Alzheimer's Disease (AD) in cerebrospinal fluid (CSF) and blood plasma, as well as assess phenserine's potential short-term effects on cognition using the FLAME Memory Composite and other cognitive sub-tests.

Participants will be enrolled at six centers across Norway. The study will also be supported by the PROTECT platform, which allows for the recruitment of individuals over 50 years of age who have demonstrated cognitive decline, making them suitable candidates for this study.

The anticipated duration of participation for each patient is 8 weeks, with the overall study expected to be completed within 9 months, accounting for a 6-month enrollment period followed by the treatment phase.

[figure not shown]
Study Population and Statistical Methods

A total of 16 participants are expected to be enrolled in this dose-ranging study. The primary population for analysis will be a modified intent-to-treat group, including all participants who received at least one dose of study medication and provided at least one follow-up exosome sample.

[figure not shown]
This study will provide critical data on the pharmacodynamic and pharmacokinetic profiles of phenserine, which will guide future research and potential therapeutic strategies for early to mild AD.

1.2. Schema

Figure 1. Study Schema

Study design, detailing the randomization of participants into two arms: the Phenserine Arm (n=12) and the Donepezil Arm (n=4). Participants in the Phenserine Arm will start at 5 mg twice daily (BD) with dose escalations at specified intervals up to 10mg three times daily (TDS).

Figure 2. FDA Framework for Pre-Clinical and Clinical AD

1.3. Schedule of Activities (SoA)**Table 1. Schedule of Activities**

	Screening (within 28 days before baseline)	Treatment Period					Safety Follow-up ¹ /EOS (within 28 days after last visit)
		Baseline	W2	W4	W6	W8	
Days \pm Visit window	-28 to 0	0	(14\pm 3)	(28\pm 3)	(42\pm 3)	(56\pm 3)	(56\pm 28)
Informed consent	X						
Demographics	X						
Medical history ²	X						
Concomitant medications	X	X	X	X	X	X	X
Vital signs	X	X	X	X	X	X	X
Physical Exam	X	X	X	X	X	X	X
Neurological Exam	X						X
ECG	X	X	X	X	X	X	X
MMSE	X						
MoCA		X				X	
CDR	X						
MRI ³	X						
Suicidal screening using C-SSRS, modified ⁴	X			X		X	X
Inclusion/Exclusion criteria	X	X					
Randomization		X					
Dispense of IMP ⁵		X	X	X	X		
Adverse events		X	X	X	X	X	
AchE sample collection		X	X	X	X	X	

Dose review (for escalation or de-escalation)			X	X	X		
Exosome Biomarker Collection		X	X	X	X	X	
Blood and CSF-based biomarkers ⁶	X					X ⁷	
PK sample collection			X	X	X	X	
Safety laboratory test ⁸	X		X	X	X	X	X
Urinalysis	X		X	X	X	X	X
FSH test ⁹	X						
Pregnancy test ¹⁰	X		X		X		
FLAME Cognitive battery		X				X	

¹ A safety follow-up visit will be conducted within ~4-weeks after the last study-drug dose for all participants who complete the study or who terminate early.

² Includes prior medication use.

³ Only if no MRI scan available within last 2 years.

⁴ The C-SSRS will only be conducted at the follow-up/EOS visit, if the patient experienced suicidal thoughts after the study treatment period.

⁵ Before any dose escalation. According to tolerability and laboratory tests, the dosage will be reassessed, and participants may need to return to the center for a reduced dose.

⁶ CSF samples will only be collected from patients who specifically consent to CSF sample collection and analysis. If CSF biomarker data are available then there is no need for a new CSF collection at screening

⁷ CSF collection at W8 is voluntary and requires an additional informed consent.

⁸ Renal and liver function will be taken every visit. Full Safety laboratory battery will be taken at screening and safety follow-up.

⁹ Women considered post-menopausal will have an FSH test to confirm their status during the screening period and prior to dosing.

¹⁰ Pregnancy testing is required for all women of childbearing potential within one day prior to receiving the first dose of study drug.

2. Introduction

Phenserine is a next generation AChE inhibitor being developed for the treatment of AD. Unlike currently marketed AChE inhibitors, it has additional mechanisms of action that also include a mediating effect on cell death pathways and anti-amyloid activity, which may confer disease-modifying effects in people with AD.

Phenserine's names, designations, and chemical structure are summarized below.

INN: Phenserine tartrate

Other Names: -eseroline phenylcarbamate

CAS No. 101246-66-6

[figure not shown]
Trade name(s): Not applicable

IUPAC name: (3a'S,8aR)-1,3a,8-Trimethyl-1H,2H,3H,3aH,8H,8aH-pyrrolo[2,3-b] indol-5-yl N-phenylcarbamate

Molecular Formula: C₂₀H₂₃N₃O₂

Molecular Weight: 337.4 g/mol

Structural Formula:

Phenserine was originally identified and developed by the United States (U.S.) National Institute of Aging (NIA), part of the U.S National Institute of Health (NIH). It has previously been evaluated in a total of 11 studies, including 2 initial safety and tolerability studies that included PK and PD assessments in healthy normal subjects. In addition, bioavailability and food effect studies were conducted to assess PK parameters of an early immediate release 10-mg tablet formulation versus an oral solution. A U.S. corporate sponsor, Axonyx Inc., subsequently purchased the rights to the compound and conducted additional clinical studies, including additional PK and safety studies using 10-mg and 15-mg tablet formulations under fasted and fed conditions in healthy subjects. In addition, eight Phase 2-3 studies were conducted in patients with probable mild-moderate AD. In total, the drug has been evaluated in over 1300 people with AD. All studies for which data are publicly available are summarized in the Investigator's Brochure.

It is imperative to address the growing global health challenge of dementia. According to the 2023 World Alzheimer's Report (1), it is anticipated that, globally, the number of people living with dementia will increase to 139 million by 2050, a 2.5-fold increase over the estimated number in 2019. Similarly, the annual costs associated with dementia are expected to more than double to \$2.8 trillion dollars by 2030, compared to US\$1.3 trillion in 2019. The World Health Organization (WHO) estimated in 2023 that there are more than 55 million people with dementia

worldwide, and that each year, there are nearly 10 million newly diagnosed cases, In addition, it is estimated that at least 15% of people aged 60 or above have Mild Cognitive Impairment (MCI), and that between 8 and 15% of these will progress to dementia each year, most commonly to AD(2). Alzheimer's disease (AD) is a devastating, progressive neurodegenerative disorder with a massive personal and financial impact on individuals, families and society. With ageing populations and the rapid rise in the number of people with AD and MCI, increasing the pipeline to accelerate the development of effective treatments is considered an urgent priority.

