Phenserine showed high and predictable oral bioavailability across the dose levels. Over the 4-fold increase in dose, AUC₀₋₂₄ values increased by ~25%. T_{max} values ranged from 1.25-1.54 hr, and t_{1/2 elim} = 6.53 hr. Erythrocyte AChE inhibition reached peak values of 12%, 23% and 46% at 2 hours postdose for the 10, 15, and 20 mg/kg dose groups, respectively, and showed a linear relationship to phenserine plasma concentrations. Other studies have demonstrated that phenserine's effects on cognition and other neuropsychiatric assessments are positively correlated with increased CSF Aβ₄₀ and sAβPP levels as well as improved regional cerebral blood flow (rCBF) and metabolic rate for glucose (rCMRglc). In addition, CSF Aβ₄₂ levels, the Aβ₄₂/40 ratio, P-tau, and T-tau correlated negatively with rCMRglc and cognition (7,8).

In a follow-on study (5) elderly but otherwise healthy volunteers were randomized to receive once daily doses of phenserine immediate release capsules at 5 mg QD, 5 mg BID, 10 mg QD, or 10 mg BID (8 subjects/group) for 6 days. There were no dose-limiting or serious adverse events (AEs) reported for any subject. In addition, there were no clinically significant findings in clinical laboratory measures or ECG assessments across all dose groups. Peak plasma concentrations increased with dose but were similar across the QD and BID dosage regimens for each dose level. In addition, AUC₀₋₂₄ values remained consistent over the 6-day treatment period confirming that drug accumulation does not occur with repeated dosing. Erythrocyte AChE inhibition of 15% and 30% were observed for the 5 and 10 mg dose groups, respectively, regardless of the once- or twice-daily dosing schedules.

A subsequent NIA-sponsored Phase 2, 12-week RCT in 72 patients indicated that phenserine (10-15 mg b.i.d.) conferred significant improvements in cognitive function and a trend towards improvement in global outcome in people receiving the higher dose, with Cohen's D effect sizes of 0.3-0.4 for symptomatic benefits (6).

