Importantly, there is clear evidence from trials with other cholinesterase inhibitors, that C_{max} is related to the severity of adverse events, and that a total daily dose spread into smaller individual doses has been an effective way of reducing the potential for adverse effects (9). Slow dose titration (10) and administering medications with food have also been important in reducing the potential for adverse events. In the current study, each participant in the phenserine arm will be titrated at 2-weekly intervals from 5 mg twice-daily to up to 10 mg 3-times daily, if tolerated. The rationale for this 45% AChEI is based on the results from several research groups that have

aimed to quantify the association between the level of cholinesterase inhibition achieved by donepezil and other ChEIs and clinical response. One of the most active group, prof Nordberg's group at Karolinska Institute, reported (11) that " the optimal CSF AChE inhibition for donepezil was over 45% ". This was related to cognitive response. Participants will also be instructed to take each dose with food.

No depressions of any blood cell lines were noted in animal toxicology studies. However, the clinical effects of phenserine on complete blood count (CBC) counts have not been reported in the literature. Nevertheless, a similar molecule based on physostigmine, heptylphysostigmine, was found to induce granulocytopenia in two studies that resulted in the suspension of further clinical trials (12).

In summary, the previous studies have shown acceptable tolerability of 15mg BID, eg Winblad et al(3) (255 patients) showed withdrawals due to side-effects in 15mg BID (5.9%) similar to that of placebo (6.1%). In Kadir et al 2008(13), including 20 patients for 3 months followed by 9M open-label, phenserine 15mgx2, ChEI-related gastrointestinal symptoms were observed in three patients, which resolved in two patients after dose reduction to 20mg/d. This is similar rates as reported for licensed doses of cholinesterase inhibitors. Thus, our interpretation is that 30mg is well tolerated.

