11.2. Appendix 2: Clinical Laboratory Tests

- The safety laboratory will monitor key hematological, biochemical, and urinary parameters throughout the trial period. Complete battery will be performed at screening and Safety follow up, for details refer to the laboratory tests SOP.
- Follow-up visits: Liver and renal function with urinalysis (dipstick) tests will be conducted to monitor participant safety and assess any potential adverse effects throughout the trial duration.
- The tests detailed in Table below will be performed by the local laboratory.
- Additional tests may be performed at any time during the study as determined necessary by the investigator or required by local regulations.

Table 7: Protocol-required Safety Laboratory Tests

Laboratory Tests	Parameters
Hematology	
 • Platelet count • Red blood cell (RBC) count • RBC indices 
 – Mean corpuscular volume (MCV) – Mean corpuscular hemoglobin (MCH) – %Reticulocytes • White blood cell (WBC) count with differential: 
 – Neutrophils – Lymphocytes – Monocytes – Eosinophils – Basophils • Hemoglobin • Hematocrit
Clinical chemistry¹	
 • Blood urea nitrogen (BUN) • Potassium • Creatinine • Sodium • Calcium • Glucose (fasting) • Vitamin B12 (total and active) • CRP • Aspartate aminotransferase (AST)/serum glutamic-oxaloacetic transaminase (SGOT) • Alanine aminotransferase (ALT)/serum glutamic-pyruvic transaminase (SGPT) • Alkaline phosphatase² • Total and direct bilirubin • Total protein

Routine urinalysis	
 • Specific gravity • pH, glucose, protein, blood, ketones, (bilirubin, urobilinogen, nitrite, leukocyte esterase) by dipstick • Microscopic examination (if blood or protein is abnormal)
Pregnancy testing	
 • Highly sensitive (serum or urine) human chorionic gonadotropin (hCG) pregnancy test (as needed for women of childbearing potential)³
○	

NOTES:

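### No blood count is scheduled while participants are on study drug, although the protocol itself leaves phenserine's effect on counts as an open question

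*Protocol*

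**What the plan says.** Table 1 of Protocol 1.3 marks a safety laboratory test at screening, at Weeks 2, 4, 6 and 8, and at safety follow-up. Footnote 8 limits what that means: renal and liver function at every visit, and "Full Safety laboratory battery will be taken at screening and safety follow-up".

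Appendix 2 (11.2) gives the same split. Its first bullet opens with "The safety laboratory will monitor key hematological, biochemical, and urinary parameters throughout the trial period" and continues "Complete battery will be performed at screening and Safety follow up, for details refer to the laboratory tests SOP". The next bullet, on follow-up visits, says "Liver and renal function with urinalysis (dipstick) tests will be conducted to monitor participant safety". Table 7 in that appendix lists haematology (white cells with differential, platelets, haemoglobin and so on) as part of the required battery.

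Three other places bear on the point:

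- Section 2.3.1 states that "the clinical effects of phenserine on complete blood count (CBC) counts have not been reported in the literature" and that a physostigmine-based relative of phenserine "was found to induce granulocytopenia in two studies that resulted in the suspension of further clinical trials". It also says "No depressions of any blood cell lines were noted in animal toxicology studies".
- Section 3.2.2 includes full blood count in the safety laboratory tests of the key secondary outcome. It also makes clearance for the next dose depend partly on safety blood tests.
- SAP 8.1 will summarise laboratory abnormalities by arm. Protocol 10.3 promises a summary of important laboratory findings by arm and dose level, without naming haematology.

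**The concern.** The protocol names a haematological uncertainty and then schedules no test that could address it during exposure. The only post-baseline count comes after the last dose, and the only earlier count comes before the first.

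Two things are at stake. The first is individual safety: phenserine is escalated at Week 2 and again at Week 4, and no count taken on drug is scheduled to inform either decision. A fall in neutrophils or platelets without symptoms, recovering before follow-up, would not be seen by the scheduled tests. The second is description: the study is meant to inform the Phase 2 dose range, but it would have no scheduled haematology data at 5 mg bd, 10 mg bd or 10 mg tds. Efficacy and biomarker estimates are not affected.

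**Working it through.** The plan states no figure to reproduce here, so the check is a cross-reading of the schedule followed by simple arithmetic.

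**Scheduled tests by visit** (Table 1 with footnote 8; Appendix 2; doses from Table 3, assuming the planned titration)

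| Visit | Phenserine dose at the visit | Liver, renal, urine | Haematology |
|---|---|---|---|
| Screening | none | yes | yes |
| Baseline | none yet | no | no |
| Week 2 | 5 mg bd | yes | no |
| Week 4 | 10 mg bd | yes | no |
| Week 6 | 10 mg tds | yes | no |
| Week 8 | 10 mg tds | yes | no |
| Safety follow-up | stopped | yes | yes |

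Scheduled on-drug counts are therefore 0 of 4 visits per participant: 0 of 12 × 4 = 48 phenserine visits and 0 of 16 × 4 = 64 visits overall.

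**Age of the screening count at each escalation.** Screening falls on day −28 to 0, and visits have a window of ±3 days.

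- Week 2: at most 28 + 14 + 3 = 45 days; at least 0 + 14 − 3 = 11 days.
- Week 4: at most 28 + 28 + 3 = 59 days; at least 0 + 28 − 3 = 25 days.

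**Longest gap between the two scheduled counts.** Follow-up is placed within one week of the last dose in Sections 4.1, 6.3 and 9, and within 28 days in Table 1 and Section 9.8.

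- One-week wording: 28 + (56 + 3) + 7 = 94 days.
- 28-day wording: 28 + (56 + 3) + 28 = 115 days.

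**How far off drug the last count can be.** Section 2.3.1 gives an elimination half-life of 6.53 hours.

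- 7 days: 7 × 24 / 6.53 = 25.7 half-lives.
- 28 days: 28 × 24 / 6.53 = 102.9 half-lives.

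These figures describe drug clearance, not recovery of counts. The documents give no recovery time, so the share of falls that would be missed cannot be calculated.

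**What on-drug counts could show.** No event rate is given, so a range is assumed. If a proportion p of phenserine participants had a detectable fall, the chance of at least one case among 12 is 1 − (1 − p)^12.

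| Assumed p | 1% | 2% | 5% | 10% | 20% |
|---|---|---|---|---|---|
| Chance of at least one case | 11% | 22% | 46% | 72% | 93% |

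With no cases in 12, the one-sided 95% upper limit is 1 − 0.05^(1/12) = 22%. Added counts could rule out only a common effect.

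**The case against.** The strongest reply has four parts.

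*The text leaves room for counts on treatment.* Appendix 2 defers detail to a laboratory SOP that is not available here. Sections 9.4 to 9.7 repeat the baseline evaluations, Section 9.3 refers back to screening, and screening includes safety laboratory tests. Section 7.1.3 also calls for electrolyte monitoring, which goes beyond liver and renal function. This makes the protocol ambiguous, but none of it names a blood count. Table 1 shows no safety laboratory test at baseline to be repeated, and footnote 8 and Appendix 2 are the specific statements. What stands is that the claim must be confined to what is scheduled.

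*The first bullet of Appendix 2 may be only a lead-in* to the specifics that follow it. That is a fair reading, so the conflict in wording is supporting evidence only. The firmer basis is Section 3.2.2, although it sets no timing for the count.

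*Prior experience is reassuring.* Animal studies showed no effect on blood cells. For the six-day repeat-dose volunteer study, Section 2.3.1 says "there were no clinically significant findings in clinical laboratory measures or ECG assessments across all dose groups". Section 2.3 reports 645 participants treated with phenserine for 6 to 12 months and review of the data by health authorities. The top daily dose of 30 mg equals the earlier 15 mg bd, and an effect absent from the literature may still have been measured. All this lowers the prior concern. However, the volunteer summaries do not mention counts, and Section 2.3.1 records the gap despite that exposure.

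*The study is too small, and other safeguards exist.* Twelve participants cannot characterise haematology by dose. Investigators may add tests, a DSMB reviews safety, and early terminators are seen within a week of stopping. On the one-week wording, the last count also falls soon after about four weeks at maintenance dose. The point about size stands and weakens the dose-ranging argument. It does not weaken the case for protecting individuals at escalation, and discretionary tests are unlikely to be prompted by a fall without symptoms.

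**Conclusion.** The concern holds. As written, the protocol schedules no blood count during treatment, so haematology is unobserved by scheduled tests at every phenserine dose level and at both escalation decisions. This should be fixed. It is a gap in safety monitoring with an inexpensive remedy and does not threaten the primary endpoint.

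The conclusion assumes that footnote 8 and Appendix 2 govern over the looser visit descriptions, and that the unseen laboratory SOP does not add counts. If the SOP does add them, the protocol still needs correcting to match. The day counts above are limits set by the visit windows, not typical values, and the probability that a real fall would go undetected is unknown.

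**What to change.** Amend footnote 8 and the follow-up bullet in Appendix 2 to add a full blood count with differential at Weeks 2, 4, 6 and 8, drawn at the venepuncture already planned in Sections 9.4 to 9.7. On the planned titration this gives one count at 5 mg bd, one at 10 mg bd and two at 10 mg tds.

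Include the Week 2 and Week 4 counts in the safety blood tests used for escalation. Results arriving after the visit can follow Section 3.2.2, which already allows the participant to be contacted and the decision revised, so dispensing need not wait. Abnormal values go through the investigator review in Section 9.15. Section 7.1 has no haematological criterion, so the sponsor should also consider a neutrophil threshold; the documents offer no basis for a particular value.

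If counts are not added, SAP 8.1 should state that on-treatment haematology is not assessed, and the opening sentence of Appendix 2 should be corrected.

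The cost is a protocol edit and 64 extra counts, 48 of them on phenserine. Assuming 3 to 5 mL per tube, four tubes take 12 to 20 mL per participant, which is 12/642 = 1.9% to 20/642 = 3.1% of the blood limit in Section 9. There will be laboratory charges and some repeat tests for isolated out-of-range values. The pre-drug reference would still be the screening count, up to 28 days before the first dose.
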